## STATEMENT OF COMPLIANCE

The trial will be conducted in accordance with International Council on Harmonisation Good Clinical Practice (ICH GCP), applicable United States (US) Code of Federal Regulations (CFR), and the <specify NIH Institute or Center (IC) > Terms and Conditions of Award. The Principal Investigator will assure that no deviation from, or changes to the protocol will take place without prior agreement from the funding agency and documented approval from the Institutional Review Board (IRB), and the Investigational New Drug (IND) or Investigational Device Exemption (IDE) sponsor, if applicable, except where necessary to eliminate an immediate hazard(s) to the trial participants. All personnel involved in the conduct of this study have completed Human Subjects Protection and ICH GCP Training.

The protocol, informed consent form(s), recruitment materials, and all participant materials will be submitted to the IRB for review and approval. Approval of both the protocol and the consent form(s) must be obtained before any participant is consented. Any amendment to the protocol will require review and approval by the IRB before the changes are implemented to the study. All changes to the consent form(s) will be IRB approved; a determination will be made regarding whether a new consent needs to be obtained from participants who provided consent, using a previously approved consent form.

## 1 PROTOCOL SUMMARY

### 1.1 SYNOPSIS

**Title:**

Noom Health for Weight Management

**Study Description:**

Overweight and obesity affect as many as one-third of the population of the United States. Excess weight represents a serious public health concern, as overweight and obesity are associated with an increased risk of medical sequelae (e.g., high blood pressure, sleep apnea, COVID-19, etc.). Although behavioral treatments for obesity are generally effective, reductions in weight are typically modest and largely not maintained over the long-term. This study will test a successful commercially available weight loss phone app (Noom Health) in comparison to a Digital Education program (Noom Digital Health) for weight loss, quality of life, psychosocial functioning, and self-reported health status. We will recruit 600 subjects and randomize them to receive Noom Health vs. Digital Control. Baseline measures will include demographics, psychosocial measures, height/weight, weight loss history/practices, health care practices/utilization, and quality of life. We will conduct remote scheduled direct entry interview and self-report questionnaire data at 8 time points (Screening/Baseline, 1 month, 4 months, 6 months, 12 months, 18 months, 24 months, and 30 months). Weight data will be collected by video observed scale. Digital scales will be provided for those who do not have access.

**Objectives:**

**Primary Objective:** The goals of the study are to use the Noom smartphone platform to help individuals with weight loss, quality of life, psychosocial functioning, and self-reported health status.

**Secondary Objectives:** We will test the efficacy of this platform against a Digital Education program in a cohort of patients.

**Endpoints:**

We will conduct remote scheduled direct entry interview and self-report questionnaire data at 8 time points (Screening/Baseline, 1 month, 4 months, 6 months, 12 months, 18 months, 24 months, and 30 months). Weight data will be collected by video observed scale. Digital scales will be provided for those who do not have access

**Study Population:**

Overweight and obese adults aged 18-60 years.

**Phase or Stage:**

*Phase II trial.*

**Description of****Sites/Facilities Enrolling****Participants:**

The team at the Icahn School of Medicine at Mount Sinai (ISMMS) is responsible for recruitment, consenting, consulting on the coaching intervention, and data collection and analysis. Research procedures are expected to occur remotely with ISMMS staff.

[figure not shown]

Description of Study	Participants will use the Noom app for 6 months of intervention and 6
Intervention/Experimental	months of maintenance (12 months total).
Manipulation:	
Study Duration:	3-5 years
Participant Duration:	30-32 months

## 1.2 SCHEMA

**Flow Diagram (randomized controlled trial)**

### 1.3 SCHEDULE OF ACTIVITIES

The schedule of activities (SOA) provided below outlines the expected activities for each research visit. Participants are expected to be enrolled in the study for 2.5 years and complete all research visits via a HIPAA compliant video platform (Zoom) and REDCap.

	Pre-screening (Pre-consent)	Visit 1 Day 1	Visit 2 Day 30 ± 42	Visit 3 Day 121 ± 42	Visit 4 Day 182 ± 42	Visit 5 Day 365 ± 42	Visit 6 Day 547 ± 42	Visit 7 Day 730 ± 42	Visit 8 Day 912 ± 42
EMR Review Eligibility	X								
Informed Consent		X							
Demographics		X							
Height, Weight,		X	X	X	X	X	X	X	X
Outcome Evaluation									
Depression, Anxiety, Stress Scale		X	X	X	X	X	X	X	X
Quality of Life Questionnaire		X	X	X	X	X	X	X	X
ASA24		X	X	X	X	X	X	X	X
Eating Disorder Examination Questionnaire		X	X	X	X	X	X	X	X
International Physical Activity Questionnaire		X	X	X	X	X	X	X	X
PROMIS Sleep Impairment		X	X	X	X	X	X	X	X
Short Form Health Survey		X	X	X	X	X	X	X	X

Brief Self-Efficacy Scale for Healthy Eating		X	X	X	X	X	X	X	X	X
Randomization		X								
Control & Experimental Interventions – Noom App vs Digital Control		X	X	X	X	X				
Adverse Events Reporting		X	X	X	X	X	X	X	X	X

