### 7.3 LOST TO FOLLOW-UP

Participants will be considered lost to follow-up if they withdraw from the study by directly contacting our research team or if they don't complete the follow-up assessments. Participants will be contacted

throughout the assessment window via phone, email, and the family/friend contact. If no contact is made during the assessment window, they will be deemed lost to follow-up.

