### 9.2 SAMPLE SIZE DETERMINATION

Mt. Sinai will use piecewise latent growth curve models with treatment as primary indicator. Using Monte Carlo simulation studies with 10,000 draws and 6 time points and 2 growth processes, Mt. Sinai evaluated sample size needed to detect significant differences on each growth process (within treatment, post-treatment follow-up). Mt. Sinai also varied missing at random patterns of missing of data at 10%, 20% and 30% increasing linearly over each timepoint. The results indicate that with 30% missing data, mean difference in BMI change of 1.2 (SD =4.5), Mt. Sinai is 85% powered to detect significant difference at 24 month follow-up with N = 600. The power increases substantially for within treatment BMI change .8 (SD =4.5), power = .942. For psychosocial outcomes, N=600 with same parameters indicated 82-90% power to find treatment effects at 24 months, assuming a .20 SD unit difference between groups. Within treatment, the same difference is powered 90-98%.

For Aim 2, Mt. Sinai assumed full information on all moderators and tested the interaction effect with a composite moderator profile of 12 indicators. The interaction between latent moderator (M) and treatment was powered at .93 and .85 with N=600, and 30% attrition for within treatment and follow-up.

For Aim 3 power analyses were based on a 13-item adherence measure adapted from the Noom Monitor (Binge Eating) study and assumes network efficiency of .75. Mt. Sinai would examine the relationship between network entropy and the outcomes, with statistical power for the regression prediction at 100% for each outcome. Mediation model of weekly regular eating is a time series mediation model and assumes latent measure of meal-snack adherence will mediate changes in weight. The calculation is based on effect size goal of .25, .5, and .75. The results of simulations suggest that power for the smallest effect size (.25) is approximately .80 with 10% missing data or less and moderate correlations between time and change in regular eating (.3) and moderate correlation between regular eating and weight outcome (.3).

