### 9.4 STATISTICAL ANALYSES

#### 9.4.1 GENERAL APPROACH

We are using a latent growth curve model (piecewise) to model separate change processes assumed during weight loss and post intervention. All models will be examined for goodness of fit, normality and linear (vs. Nonlinear) change. Best fit models will be interpreted for primary effects.

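### Do the overlapping ±42-day visit windows, and the silence on nominal versus actual time, undermine the 6-month growth-model comparison?

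*Combined protocol and SAP*

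**What the plan says.** The schedule in Section 1.3 puts consent, baseline and randomisation at Visit 1 on Day 1, and gives Visits 2 to 8 one common tolerance. The three visits that matter here are "Visit 2 Day 30 ± 42", "Visit 3 Day 121 ± 42" and "Visit 4 Day 182 ± 42". Visit 4 carries the first primary hypothesis in Section 9.1, the 6-month comparison of weight loss.

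Section 7.3 makes the window operational: "If no contact is made during the assessment window, they will be deemed lost to follow-up". The synopsis describes the assessments as scheduled: "We will conduct remote scheduled direct entry interview and self-report questionnaire data at 8 time points".

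On the analysis side, Section 9.2 describes the power work as "Using Monte Carlo simulation studies with 10,000 draws and 6 time points and 2 growth processes". Section 9.4.1 chooses a piecewise latent growth curve "to model separate change processes assumed during weight loss and post intervention". Section 9.4.2 requires RMSEA below .05 before a model is interpreted and allows non-linear terms if fit calls for them. Section 9.4.8 says only that data are laid out by person and period. None of these sections defines the time score.

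**The concern.** Two things look loose. First, a contact between Days 140 and 163 lies in the windows of both Visit 3 and Visit 4, with no stated minimum spacing and no written rule on which visit it counts for. A Visit 2 window that opens before randomisation looks like an error.

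Second, a growth model needs a time axis. With scheduled-visit scoring, a Visit 4 weight taken anywhere from Day 140 to Day 224 is treated as a Day 182 weight, although that span covers both the end of the intervention and the start of maintenance. With actual-day scoring it is not. If the two gave materially different 6-month estimates, the choice would be one more left to the analyst, on a primary comparison, in a trial where participants know their arm.

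**Working it through.** **Windows.** Inputs are the target days in Section 1.3; each window is target − 42 to target + 42, which is 2 × 42 + 1 = 85 days.

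| Visit | Target | Window |
|---|---|---|
| 2 | 30 | -12 to 72 |
| 3 | 121 | 79 to 163 |
| 4 | 182 | 140 to 224 |
| 5 | 365 | 323 to 407 |
| 6 | 547 | 505 to 589 |
| 7 | 730 | 688 to 772 |
| 8 | 912 | 870 to 954 |

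Only Visits 3 and 4 overlap: 163 − 140 + 1 = 24 days, and 24/85 = 28%. All other adjacent follow-up windows are separated, the closest being Visits 2 and 3, with 79 − 72 − 1 = 6 clear days.

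**Visit 2 lower limit.** 30 − 42 = Day -12. Section 1.3 places consent and randomisation on Day 1, and Section 10.1.1.2 bars collecting further information before signed consent. No follow-up can fall before Day 1. The negative day is a by-product of writing one tolerance for all visits.

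**Visit label and Section 7.3.** Each visit is numbered, booked and completed by Zoom and REDCap, so an assessment belongs to the visit for which it was booked. Section 7.3 asks whether contact was made within the window. A day that lies in two windows does not make that question unanswerable, so the two sections do not conflict.

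**Time score.** Section 9.2 simulates a fixed set of time points with missingness rising from one to the next. RMSEA, the criterion in Section 9.4.2, ordinarily goes with growth models whose time loadings are fixed and common to all participants. Both point to scheduled-visit scoring, though neither says so.

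**Scale, conditional on assumptions.** The plan's planning figure is "within treatment BMI change .8 (SD =4.5), power = .942", read here as a between-arm difference in BMI change. Assume the difference builds up linearly from Day 1 to Day 182 and that Visit 4 is shifted by *k* days for everyone in both arms. Reading the difference straight off Visit 4, the error is 0.8 × *k* / 181.

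- *k* = 14: 0.8 × 14 / 181 = 0.062 BMI; 0.062 / 4.5 = 0.014 SD.
- *k* = 42, the edge of the window: 0.8 × 42 / 181 = 0.186 BMI; 0.186 / 4.5 = 0.041 SD.

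Days scattered evenly around the target average out under linearity. Section 4.3 expects most participants to reach maximal loss within 3 to 4 months, before the Visit 4 window opens; a flatter course there makes the error smaller than these figures.

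**The case for a change.** The strongest case is timing that differs between arms. Participants are unblinded and only Noom Health has coaches, so one arm might be assessed systematically earlier. The error is then the shift multiplied by that arm's own rate of loss, which can exceed the difference in rates. For illustration, assume baseline BMI 33, linear loss of 5% to 10% (the range in Section 4.3) and one arm 14 days off target. The error would be 1.65 × 14 / 181 = 0.13 to 3.3 × 14 / 181 = 0.26 BMI, against a planned 0.8. That would not be trivial.

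What stands is that the time score is unstated and that timing by arm deserves a look. What does not stand is any claim that a bias exists. The same research team assesses both arms on the same schedule, nothing in the documents suggests a difference, and the baseline BMI and the shift are assumptions. Linear loss up to Day 182 is also at odds with Section 4.3.

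Prescribing actual-day scoring would not be a clear gain either. If loss is front-loaded and the model fits one straight slope to Day 182, the wrong mean shape can dominate, and an actual-day fit may lie further from the truth than a scheduled-visit fit. Section 9.4.2 already deals with shape by allowing non-linear terms.

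**Conclusion.** No change is needed. The overlap of 24 days and the Day -12 limit are exact, but the first is settled by the scheduled visit and the second cannot occur. The unstated time score is a true omission that a competent analyst fills in the ordinary way: scheduled-visit scoring for the model judged by RMSEA, assessments kept under the visit for which they were booked, and actual assessment days inspected by visit and arm before the results are read.

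No size of bias can be claimed, because the documents give no distribution of visit days. Under linear divergence and timing common to both arms, even a shift to the edge of the Visit 4 window comes to about 0.04 SD. This conclusion assumes that assessment dates are recorded, as they would be in REDCap, and that timing is broadly alike in the two arms. A marked arm difference in actual days would reopen the question. The manual of procedures mentioned in Section 10.1.10 is not among the documents and may already hold the filing rule.

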## 2 INTRODUCTION

### 2.1 STUDY RATIONALE

The goals of the study are to use the Noom smartphone platform to help individuals with weight loss, quality of life, psychosocial functioning, and self-reported health status. In addition, we will test the efficacy of this platform against a Digital Education program in a cohort of patients.

We will conduct a large test (n=600) where participants are randomized to receive Noom Health vs. Digital Control (Noom Digital Health). Baseline measures will include demographics, psychosocial measures, height/weight, , weight loss history/practices, health care practices/utilization, and quality of life. We will conduct remote scheduled direct entry interview and self-report questionnaire data at 8 time points (Screening/Baseline, 1 month, 4 months, 6 months, 12 months, 18 months, 24 months, and 30 months). Weight data will be collected by video observed scale. Digital scales will be provided for those who do not have access.

### 2.2 BACKGROUND

Overweight and obesity have reached epidemic proportions in the United States. Excess weight represents a serious public health concern, as overweight and obesity are associated with an increased risk of medical sequelae (e.g., high blood pressure, sleep apnea, COVID-19, etc.). Although behavioral treatments for obesity are generally effective, reductions in weight are typically modest and largely not maintained over the long-term.

Behavioral weight loss programs are typically provided with weekly nutritional counseling because of the numerous required changes to diet and physical activity; however, this type of intervention is costly and requires the availability of trained professionals with advanced degrees. A smartphone app to translate behavioral weight loss principles into a digestible and manageable intervention helps to overcome limitations such as costs, availability of trained professionals, and time-burden and scalability that make behavioral weight loss less practical and available. The Noom platform improves the accessibility of expert guidance for individuals interested in weight loss and facilitates maintenance through low-burden smart phone engagement.

### 2.3 RISK/BENEFIT ASSESSMENT

#### 2.3.1 KNOWN POTENTIAL RISKS

- Anxiety related to eating or change in weight status
- Emotional discomfort during assessments
- Possible loss of confidentiality

#### 2.3.2 KNOWN POTENTIAL BENEFITS

There are no anticipated direct benefits to participants. Some participants may improve their diet/exercise, and data from the study may help to identify individuals who benefit from a behavioral weight loss app in comparison to other interventions.

With increasing numbers of individuals with overweight and obesity, and few effective behavioral treatment options, understanding factors that influence outcomes could be broadly beneficial to society.

### 2.3.3 ASSESSMENT OF POTENTIAL RISKS AND BENEFITS

Participants may feel some anxiety related to the lifestyle changes that the intervention asks of them. Noom coaches are trained in managing these difficult situations as part of a standardized Noom Coach Academy lead by licensed clinical psychologist ([name]) who maintains the academy training and regulation. Participants are free to end their participation at any point in the study.

Participants will be told that they are free to not respond or to terminate involvement with the assessment at any time, with no adverse consequences. If a participant appears to be distressed during assessments, research staff will halt the interview and offer to proceed at another time. The interview will only recommence when and if the participant reports feeling capable of doing so. The interviews during the course of the study involve no specific risk or discomfort beyond those of a standard clinical interview. Interviews will be conducted by experienced and well-trained staff sensitive to these issues.

There is a slight risk that research records (questionnaires, consents) might be obtained by persons not authorized to do so. There is a slight risk that research data files might be compromised, and obtained or viewed by unauthorized persons. As described in the data storage section, we have secure databases that will store de-identified data. Only trained research personnel will have access to these files. Noom will have access to subjects' PHI including name, contact info, and demographics. However, Mount Sinai IT security has assessed the risk of potential PHI loss through previous similar work with Noom (IRB-16-01047).

## 3 OBJECTIVES AND ENDPOINTS

OBJECTIVES	ENDPOINTS	JUSTIFICATION FOR ENDPOINTS
Primary		
To test the comparative efficacy of Noom Health vs. Noom Digital Health for weight loss, quality of life, psychosocial functioning, and self-reported health status.	We will conduct remote scheduled direct entry interview and self-report questionnaire data at 8 time points (Screening/Baseline, 1 month, 4 months, 6 months, 12 months, 18 months, 24 months, and 30	Hypothesis 1: Noom Health users will show 6 month efficacy relative to Noom Digital Health for weight loss at post-intervention.  Hypothesis 2: Noom Health users will show long-term (12 Month) efficacy relative to Noom Digital Health.

OBJECTIVES	ENDPOINTS	JUSTIFICATION FOR ENDPOINTS
	months). Weight data will be collected by video observed scale. Digital scales will be provided for those who do not have access.	
Secondary		
To compare potential moderators of treatment response in Noom Health vs. Digital Health subjects.	We will conduct remote scheduled direct entry interview and self-report questionnaire data at 8 time points (Screening/Baseline, 1 month, 4 months, 6 months, 12 months, 18 months, 24 months, and 30 months). Weight data will be collected by video observed scale. Digital scales will be provided for those who do not have access.	Hypothesis 1: Clinical Profile (composite moderator) will show significant interaction with treatment condition, demonstrating that individuals with a more severe profile (older, less support, more health conditions, more psychosocial problems) will benefit more from Noom Health than Digital Control.  Hypothesis 2: Weight suppression (absolute difference between highest and current weight) will moderate efficacy of Noom Health vs. Digital Education.
Tertiary/Exploratory		
To identify within treatment mechanisms of change among Noom Health group.		Hypothesis 1: Time series Bayesian belief network model of adherence will predict (a) study dropout, (b) successful weight loss, (c) quality of life.  Hypothesis 2: Regular eating will mediate treatment effects of weight loss over time.  Hypothesis 3: Self-efficacy of weight loss will mediate Noom Health vs. Noom Digital Health effects at post treatment and 12 month follow-up.

## 4 STUDY DESIGN

### 4.1 OVERALL DESIGN

The study will: (a) test the Noom app in coach led groups with individuals interested in weight loss to determine if it significantly improves weight loss, quality of life, psychosocial functioning, and self-reported health status compared to a control.

We will use a randomized-controlled design comparing the Noom app administered in groups (6 months) to Digital Control with 6 months active maintenance in both groups. The proposal allows for a critical test of effect of Noom on relevant outcomes in the population.

All participants will complete a brief survey indicating that they would like to be contacted and includes a study description and availability. Then they will complete informed consent via a HIPAA-compliant videoconference (Zoom) and questionnaires on REDCap. Eligible participants will be randomized to one of two groups for 6 months intervention and 6 months maintenance (12 months of intervention): (1) Noom app with coaching (Noom Health; n=300), or (2) Digital Control (Noom Digital Health; n=300). We anticipate screening 684 subject to reach our recruitment goal of 600.

Participants' procedures:

- screening survey to determine eligibility and Baseline/Pre-intervention Zoom call
- Assessments: 24 hour recall interview, EDE-Q, Q-LES-Q-SF, IPAQ, Brief Self-Efficacy Scale for Healthy Eating, DASS, SF-36, PROMIS, Demographics and Smartphone Comfort

Intervention:

Noom Health participants will use Noom for 6 months of intervention and 6 months of maintenance (12 months total). Participants will use the app multiple times per day to log eating episodes (the number of episodes will vary by person). The features include diet, physical activity, and weight tracking, a social media group in the app, access to coaches, and personalized coach feedback. Coaches will interact with participants directly through the app. Participants will be encouraged to use the app for 6 months after intervention to maintain weight loss, with goal to maintain weight.

Noom Digital Health participants will use a limited version of Noom for 6 months of intervention and 6 months of maintenance (12 months total). The features include diet, physical activity, and weight tracking. Weight loss advice will be given once a week. Participants will use the app multiple times per day to log eating episodes (the number of episodes will vary by person). the app for 6 months after intervention to maintain weight loss, with goal to maintain weight.

Acceptability/Satisfaction assessments: During the intervention, we will send a 7-point Likert-type scale at monthly intervals Noom Health participants to assess satisfaction with the Noom app. For those in the Noom Digital Health condition, we will give a one question assessment at the same time points to indicate participants are still enrolled in research procedures.

Follow-up visits (1 month, 4 months, 6 months, 12 months, 18 months, 24 months, and 30 months): 24-hour dietary recall interview, EDE-Q, Q-LES-Q-SF, IPAQ, Brief Self-Efficacy Scale for Healthy Eating, DASS, SF-36, PROMIS, Demographics and Smartphone Comfort.

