#### 5.2 EXCLUSION CRITERIA

- Contraindication to smartphone use (e.g., seizures from prior smartphone use, do not own a smartphone).

- Acute suicide risk
- Pregnancy
- Current and planned breastfeeding\*

Individuals who are pregnant should not participate in a medically unsupervised weight loss program due to the risks associated.

\* Added after recruitment closed

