## 6 STUDY INTERVENTION(S) OR EXPERIMENTAL MANIPULATION(S)

### 6.1 STUDY INTERVENTION(S) OR EXPERIMENTAL MANIPULATION(S) ADMINISTRATION

#### 6.1.1 STUDY INTERVENTION OR EXPERIMENTAL MANIPULATION DESCRIPTION

As approved in the prior Ideate protocol, participants will be randomized to one of the groups for 6 months intervention and 6 months maintenance: (1) Noom app with coaching, administered in a group format (Noom Health; n=300), or (2) Noom Digital Health (n=300).

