## 6.2 FIDELITY

### 6.2.1 INTERVENTIONIST TRAINING AND TRACKING

Noom Coaches will be trained to monitor the safety of their participants. Additionally, in the introductory material given to all participants, information about how to identify and report a crisis will be outlined. This is to safeguard participants in the event there is a problem with the facilitator. Since this is a non-clinical population (obese individuals without serious psychopathology) and Noom has never had any incidents with their typical overweight population, we do not anticipate this will be a problem. In the event a Coach discovers one of their group members has a serious psychiatric condition (e.g., severe eating disorder, substance dependence), he/she will be instructed to alert Noom and Mt. Sinai immediately via a shared e-mail address (e.g., [contact]). These incidents will be dealt with on a case-by-case basis and the absolute minimal course of action will be to contact the identified participant with relevant psychoeducational material and/or information about where they can go to receive help.

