## 9 STATISTICAL CONSIDERATIONS

### 9.1 STATISTICAL HYPOTHESES

- Primary Endpoint(s):

Hypothesis 1: Noom Health users will show 6 month efficacy relative to Noom Digital Health for weight loss at post-intervention.

Hypothesis 2: Noom Health users will show long-term (12 Month) efficacy relative to Noom Digital Health.

- Secondary Endpoint(s):

Hypothesis 1: Clinical Profile (composite moderator) will show significant interaction with treatment condition, demonstrating that individuals with a more severe profile (older, less support, more health conditions, more psychosocial problems) will benefit more from Noom Health than Noom Digital Health.

Hypothesis 2: Weight suppression (absolute difference between highest and current weight) will moderate efficacy of Noom Health vs. Noom Digital Health.

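### Only Noom Health is delivered in coach-led groups, but the power calculation and primary model treat all participants as independent; if outcomes correlate within coach or group, the primary standard errors are too small

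*Combined protocol and SAP*

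**What the plan says.** **Delivery.** Section 4.1 sets out to "test the Noom app in coach led groups with individuals interested in weight loss to determine if it significantly improves weight loss" and describes group administration as lasting 6 months. It lists among the Noom Health features "a social media group in the app, access to coaches, and personalized coach feedback". Section 6.1.1 describes the arm as "Noom app with coaching, administered in a group format (Noom Health; n=300", and 6.2.1 speaks of a coach's own group: "In the event a Coach discovers one of their group members has a serious psychiatric condition". For the control arm, 4.1 says only: "The features include diet, physical activity, and weight tracking. Weight loss advice will be given once a week". No coach or group is listed there. Allocation is 300 to each arm.

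**Hypotheses.** Section 9.1 has two primary hypotheses. The first is "Noom Health users will show 6 month efficacy relative to Noom Digital Health for weight loss at post-intervention"; the second concerns 12 months.

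**Power.** Section 9.2 reports a simulation of a piecewise latent growth curve with treatment as the main predictor. It uses six time points, two growth processes, and up to 30% missing data that rises linearly over time points. Stated power is 85% for a BMI difference of 1.2 (SD 4.5) at 24 months, and .942 for a within-treatment difference of 0.8 (SD 4.5).

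**Analysis.** Sections 9.4.1–9.4.2 use the same kind of model for the primary endpoints. The sensitivity analyses in 9.3 concern missing data only. The one mention of robust estimation, in 9.4.2, is an optional step prompted by fit, outliers and potential subgroups. None of these sections names a coach or group term, an ICC, a design effect or a clustered variance.

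**The concern.** This is a partially nested design: participants in one arm share coaches and an in-app group, and participants in the other share neither. Randomizing individuals does not remove the problem, because the correlation arises after randomization through shared delivery. If some coaches or groups do better than others, 300 Noom Health participants carry less information than 300 independent people, and a single-level model does not see this.

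The consequence falls on the primary treatment effects. Confidence intervals would be too narrow and the power in 9.2 too high. Type I error would exceed its nominal level under a null in which coach or group effects vary but average zero. That is a different null from one in which coaching does nothing at all. A borderline 6- or 12-month result could not be judged, because the plan neither measures nor bounds the correlation.

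**Working it through.** **Can the stated power be reproduced?** Not exactly. Alpha, sidedness, growth variances and within-person correlations are not given. A two-sample normal approximation at an assumed two-sided 0.05, difference 1.2 and SD 4.5, gives 90.4% with 300 per arm, 85.3% with 255 and 78.0% with 210. So 85% is plausible with no allowance for clustering. For the 0.8 difference the same formula gives 58.6% with 300 per arm, against the stated 94.2%, so that figure rests on growth-model assumptions that are not shown. Both stated powers are therefore taken as given below.

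**Assumptions, not in the documents.** Two-sided alpha 0.05; m = 10–30 people per coach or group; ICC 0.01–0.05. At 6 and 12 months, 0–13% missing. A rise that is linear in months to 30% at month 30 gives 6/30 × 30% = 6% and 12/30 × 30% = 12%. At 24 months, 30% missing, as in 9.2.

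**Formulas.** With r the fraction retained, the design effect is DE = 1 + (r·m − 1)·ICC in Noom Health and 1 in control. The variance ratio is v = (1 + DE)/2 and the SE ratio is √v. Type I error of the unclustered test is 2·[1 − Φ(1.96/√v)]. Power with the correct SE is Φ((1.96 + z)/√v − 1.96), where z = Φ⁻¹(stated power): 1.036 for 85% and 1.572 for 94.2%.

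**Primary time points (6 and 12 months).**

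| m, ICC | missing | v | SE ratio | type I error | 94.2% becomes |
|---|---|---|---|---|---|
| 10, 0.01 | 13% | 1.039 | 1.02 | 5.4% | 93% |
| 10, 0.01 | 0% | 1.045 | 1.02 | 5.5% | 93% |
| 30, 0.05 | 13% | 1.628 | 1.28 | 12.4% | 79% |
| 30, 0.05 | 0% | 1.725 | 1.31 | 13.6% | 77% |

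Worked top row: DE = 1 + (0.87 × 10 − 1) × 0.01 = 1.077, so v = 2.077/2 = 1.0385.

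Worked bottom row: DE = 1 + 29 × 0.05 = 2.45, so v = 3.45/2 = 1.725. Power is Φ(3.532/1.313 − 1.96) = Φ(0.73) = 77%.

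**24 months, 30% missing, group effect persisting in full.**
- m 10, ICC 0.01: v = 1 + 6 × 0.01/2 = 1.030; 85% becomes 84.0%.
- m 20, ICC 0.05: v = 1 + 13 × 0.05/2 = 1.325; 85% becomes 74.0%.
- m 30, ICC 0.05: v = 1 + 20 × 0.05/2 = 1.500; 85% becomes 68.7%.

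**24 months, group effect halved.** With total variance unchanged, ICC 0.05 becomes 0.05/4 = 0.0125.
- m 20: v = 1 + 13 × 0.0125/2 = 1.081; 85% becomes 82.2%.
- m 30: v = 1 + 20 × 0.0125/2 = 1.125; 85% becomes 80.6%.

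**Check by simulation.** Null trials were simulated with a piecewise growth curve: 8 visits, knot at 6 months, dropout rising to 30% at month 30, 10,000 trials per setting, and the group effect on the 0–6-month slope. Over the same corners, ignoring groups gave type I error of 5.8%–12.5% at 6 and 12 months. A cluster-robust SE gave 4.8%–5.3%. At ICC 0 both gave 5.0%–5.2%. This simulation treated the covariance as known. The Satterthwaite small-sample correction was checked only for a difference in means, where it gave 4.8%–5.2%.

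**The case against.** The strongest reply is that the size is unknown and could be trivial. Group size, number of coaches, group stability and ICC appear nowhere in the documents. Sections 6.1.1 and 6.3 refer to a prior Ideate protocol and 10.1.10 to a manual of procedures; neither is available here, and either may give them. What the documents do say points to a low ICC. Feedback is personalized (4.1), and according to 2.3.3 "Noom coaches are trained in managing these difficult situations as part of a standardized Noom Coach Academy". At m = 10 and ICC 0.01 the SE changes by about 2%. This objection stands, and it is why the point is conditional.

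A second reply concerns 24 months. Group delivery is described for 6 months, so the 85% figure refers to a time 18 months later. The background in 2.2 says that weight reductions are largely not maintained. Fading is plausible, and the 9.1 primary hypotheses stop at 12 months. This also stands.

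A third reply is that coach or group identifiers may not exist. Section 10.1.9.1 does not list them, although scheduled coach check-ins are counted for adherence. The fix therefore needs a fallback.

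None of these replies supplies a reason to assume an ICC of exactly zero, which is what the planned model does.

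**Conclusion.** The point holds in conditional form. Whenever the within-group ICC in Noom Health exceeds zero, the planned model understates the standard error of the 6- and 12-month treatment effects, and the 9.2 power is too high. Under the assumed ranges the SE ratio is about 1.02–1.31, type I error about 5.4%–13.6%, and the 94.2% becomes about 93%–77%. At ICC 0 nothing changes.

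A reader might infer more than the documents support:

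- **That type I error is inflated to a known degree, or that the trial is underpowered.** The upper values come from an assumed corner that the documents' own description of coaching makes less likely, and the baseline power could not be verified.
- **That the 24-month power is 69%.** That needs 30% missing, m = 30, ICC 0.05 and full persistence. If the effect halves, it is about 81%–82% at m 20–30.
- **That one 30%-missing correction (SE ratio 1.015–1.225) serves all time points.** Missingness in 9.2 rises over time, so this understates the range at 6 and 12 months.
- **That the moderator tests in 9.4.3 are equally affected.** With a moderator unrelated to group, a simulated interaction test that ignored groups stayed at 5.1%–5.4%.

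**What to change.** In 9.4.1–9.4.2, before outcomes are analysed by arm, prespecify cluster-robust standard errors with small-sample (Satterthwaite-type) degrees of freedom for the primary treatment effects. Cluster on the coach or group first assigned, at coach level if groups sit within coaches, with each control participant as a cluster of one. Report the ICC, the number of clusters and their sizes. If there turn out to be very few coaches, say that the corrected test remains somewhat liberal: simulated type I error was 5.7% with 6 coaches and 7.5% with 3, at ICC 0.05.

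If identifiers cannot be retrieved from Noom, report a sensitivity analysis that inflates the SE over a stated range of ICC and group size, using the numbers retained at each time point. Under the assumptions here that is about 1.02–1.31 at 6 and 12 months.

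In 9.2, state that the power assumes no within-group correlation, or give it for a stated ICC, group size and degree of persistence.

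The cost is SAP wording, retrieval of coach or group identifiers, somewhat wider intervals and lower stated power. The footnote in 5.2, "Added after recruitment closed", shows that enrolment is over, so the change serves interpretation only and adds no participants or visits.
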